1.1 Background

1.1.1 Squamous cell carcinoma of the head and neck (SCCHN)

While localized and locoregional SCC of the head and neck (HNSCC) can be cured with surgery, radiation, or chemoradiation, a substantial number of patients will develop recurrent or distant metastatic disease after definitive locoregional therapy. These recurrences are associated with a poor overall prognosis¹², and the median overall survival in patients with metastatic SCC of the head and neck is under a year even with intensive combination chemotherapy¹³. The addition of monoclonal antibodies targeting the epidermal growth factor receptor (EGFR) to chemotherapy improves these outcomes somewhat, but these multi-agent combinations often induce significant treatment-associated toxicity that negatively impacts quality of life. As a result of the limited efficacy of standard of care treatment options, 11,500 patients die every year from squamous cell carcinoma of the oral cavity and the oropharynx in the United States alone¹⁴.

1.1.2 FDA approved immunotherapy in SCCHN

1.1.2.1 Anti-PD1 Antibodies

The anti PD-1 antibodies pembrolizumab and nivolumab have been approved by the FDA for the treatment of chemotherapy refractory recurrent / metastatic SCCHN. Although these agents can induce durable, objective tumor responses in both HPV positive and HPV negative tumors, response rates are low, ranging from 12-18%^{2,3}. Anti-PD-1 antibodies have been well tolerated with only 1 in 8 SCCHN patients experiencing grade 3 or higher adverse events. PD-1 and PD-L1 treatment failures in advanced solid tumors have been associated with inadequate intratumoral inflammatory immune responses¹⁵ and an excess of regulatory cells in the tumor microenvironment¹⁰.

1.2 Investigational Agents

1.2.1 tavo-EP

tavo-EP: Background

Tavokinogene telseplasmid with electroporation (tavo-EP) is a gene therapy approach to inducing stable intratumoral expression of the pro-inflammatory cytokine IL-12. Interleukin-12 (IL-12) is an anan endogenous, 70 kilodalton protein consisting of two subunits linked by a disulfide bond¹⁶. It is a potent pleotropic cytokine, capable of driving cell-mediated immunity through multiple parallel mechanisms, including activation of NK cells and cytotoxic T lymphocytes (CTLs) as well as inhibition of regulatory T cells and myeloid-derived suppressor cells (MDSCs)¹⁶⁻¹⁸. Also, as a potent inducer of interferon-gamma (IFN- γ), IL-12 can drive upregulation of antigen processing and presentation machinery (APM) within tumors.

tavo-EP: Pre-Clinical Data

For a thorough discussion of the pharmacology and preclinical background of tavokinogene telseplasmid, refer to the tavo Investigator's Brochure, Section 4.0

Clinical trials of tavo-EP monotherapy

tavo-EP: Safety

Overall, 96 patients (5 patients with squamous cell carcinoma of the head and neck) have been treated with monotherapy tavo-EP. In general, treatment has been well tolerated and transient,

grade 3 procedural pain has been the only observed grade 3 or higher adverse event. A summary of all grade treatment associated AEs seen in over 5% of patients and all grade 3 or higher AEs (N = 96) is given in **Table 1-1**. One SAE potentially related to monotherapy was cellulitis in one patient (1/96) that resolved with antibiotics. Additionally, one patient with head and neck cancer died from a tumoral bleeding episode involving a lesion that was distant from any treatment site. The patient's death was unrelated to treatment on study in the opinion of the treating investigator.

Table 1-1All grade treatment associated AEs seen in over 5% of patients and all grade 3 or higher AEs (N = 96)

Category	Adverse Reaction	Gr 1-2	Gr 3-4	Grade 5	All Grades
Reactions at Treatment Site	Procedural Pain	47.9%	5.2%	-	53.1%
	Inflammation	12.5%	-	-	12.5%
	Discoloration	11.5%	-	-	11.5%
	Bruising	5.2%	-	-	5.2%
Skin	Pruritus	5.2%	-	-	5.2%
	Cellulitis	5.2%	2.6%	-	5.2%
Constitutional	Fatigue	5.2%	-	-	5.2%
Any Related AE		61.5%	5.2%	-	66.7%

tavo-EP: Safety Data in SCCHN

Intratumoral injection of tavo-EP is currently under investigation in metastatic melanoma. A Phase I trial in melanoma was conducted involving seven dosing cohorts with a total of 24 patients. Patients received one cycle consisting of three days of treatment. Maximum total plasmid injected per visit ranged from 0.2-6 mg, at concentrations ranging from 0.1-1.6 mg/mL. A dose proportional increase in IL-12 protein expression compared to pretreatment in biopsied tumors was seen in all patients with no significant IL-12 spillage into circulation. Most (76%) electroporated lesions demonstrated greater than 20% necrosis at the time of follow-up biopsy or excision performed between 3 and 31 days after the last injection. Four of 19 patients who had distant disease had evidence of distant responses including 3 complete responses in patients with progressive metastatic disease. Of these patients, 2 patients had not had any subsequent systemic therapy while 1 patient had received dacarbazine following tavo-EP therapy. All three complete responses occurred in the setting of patients with disseminated progressive cutaneous lesions. No dose related or treatment related toxicity was seen except for transient pain and discomfort at the injection site²².

In a3 part, phase II multicenter study of intratumoral tavo-EP (0.5 mg/mL) in subjects with in-transit or cutaneous melanoma, the primary objectives of the first two study parts (Main and Addendum) were to assess the overall response rate (CR + PR) by either investigator modified skin Response Evaluation Criteria in Solid Tumors (msRECIST) or derived msRECIST. The trial has enrolled 51 subjects (Main =30, Addendum = 21). Efficacy data with tavo-EP as monotherapy with different dosing regimens showed a best overall response rate (BORR) of 25% to 34% as

well as 38.5 to 50.0% observed regression of distal untreated lesions. Moreover, subjects who received intratumoral tavo-EP and later went on to receive an anti-PD-1 antibody demonstrated a high PD-1-associated response rate (64% complete response [CR] + partial response [PR]). Interestingly, subjects who received an anti PD-1 antibody with no intervening therapy post intratumoral tavo-EP had a BORR of 75% (CR+PR).

Clinical data for tavo-EP in combination with pembrolizumab

Safety

Intratumoral tavo-EP was administered in combination with pembrolizumab in 22 advanced melanoma patients as part of a phase 2 clinical trial. The only grade 3 or higher adverse events observed were treatment site reactions and, in 1 patients, a transient grade 3 AST elevation. All adverse events seen in > 10% of patients treated with tavo-EP in combination with pembrolizumab and all grade 3+ AEs (N = 22) are given in **Table 1-3**.

Table 1-3All AEs seen in > 10% of patients treated with tavo-EP in combination with pembrolizumab and all grade 3+ AEs (N = 22)

Category	Adverse Reaction	Grade 1-2	Grade 3-4	Grade 5	All Grades
Reactions at Treatment Site	Pain	45.5%	9.1%	-	54.5%
	Cellulitis	-	4.5%	-	4.5%
Skin	Pruritus	22.7%	-	-	22.7%
	Rash	18.2%	-	-	18.2%
Constitutional	Fatigue	63.6%	-	-	63.6%
Respiratory	Cough	13.6%			13.6%
	Nausea	31.8%	-	-	31.8%
Gastrointestinal	Diarrhea	13.6%	-	-	13.6%
	Constipation	13.6%			13.6%
Musculoskeletal	Myalgia	22.7%	-	-	22.7%
	Arthralgia	13.6%	-	-	13.6%
	Peripheral Edema	13.6%	-	-	13.6%
Neurological	Dizziness	27.3%	-	-	27.3%
	Headache	18.2%	-	-	18.2%
Labs	Increased AST	4.5%	4.5%	-	9.1%
	Increased Creatinine	13.6%	-	-	13.6%

tavo-EP: Efficacy in Melanoma in combination with aPD-1

The ongoing combination therapy study (tavo-EP with pembrolizumab; CC 15852/OMS 1102) in subjects with low TILs showed a BORR of 50% (11/22); a CR of 41% (9/22); a disease control rate (DCR; CR + PR + stable disease [SD]) of 59% (13/22); progression free survival (PFS) of 57% at 15 months; and duration of response (DOR) of 100% (11/11) (Algazi, Tsai et al. 2016; Algazi, Tsai et al. 2016 AACR; Algazi 2017). These results are highly promising, since the eligible population are predicted to not responder to anti-PD-1 therapy alone.

1.2.2 Epacadostat

IDO Background

Inhibition of Indoleamine 2,3-Dioxygenase 1 as a Target for Cancer

Recent interest has focused on the role of IDO1 as a mechanism of induction of tolerance to malignancy²⁴. Indoleamine 2,3-dioxygenase 1 is a heme-containing, monomeric oxidoreductase that catalyzes the degradation of the essential amino acid tryptophan to N-formyl-kynurenone. Kynurenone can be subsequently metabolized through a series of enzymatic steps to nicotinamide adenine dinucleotide. Indoleamine 2,3-dioxygenase 1 is the first rate-limiting enzyme in one of the breakdown pathways of tryptophan. In another pathway, tryptophan hydroxylase catalysis of tryptophan leads to the formation of serotonin and melatonin.

The expression and activity profiles of IDO1 are distinct from those of tryptophan dioxygenase, an enzyme predominantly expressed in liver that catalyzes the same enzymatic reaction as IDO1 and maintains proper tryptophan balance in response to dietary uptake. In contrast to tryptophan dioxygenase, IDO1 is expressed in a variety of tissues, with particularly high levels found in areas of contact with potential sources of immune challenge (eg, gut, respiratory tract, placenta, spleen), consistent with a role for regulating tryptophan metabolism in a local microenvironment²⁵. Within the immune system, IDO1 activity is specifically induced in cells such as DCs and macrophages at localized sites of inflammation²⁶.

Indoleamine 2,3-dioxygenase 1–driven oxidation of tryptophan results in a strong inhibitory effect on the development of T-cell–mediated responses by blocking T-cell activation and inducing T-cell apoptosis²⁷. Both the reduction in local tryptophan levels and the production of tryptophan catabolites that are inhibitory to cell proliferation contribute to the immunosuppressive effects²⁸. Indoleamine 2,3-dioxygenase 1 activity also promotes the differentiation of naive T cells to cells with a regulatory phenotype (Treg)²⁹. Because increased Treg activity has been shown to promote tumor growth and Treg depletion has been shown to allow an otherwise ineffectual antitumor immune response to occur³⁰, IDO1 expansion of Treg may provide an additional mechanism whereby IDO1 could promote an immunosuppressive environment.

The biological relevance of IDO1 inhibition to immune tolerance was first demonstrated when it was shown that treating mice with a small molecule inhibitor of the IDO1 pathway, 1 methyl tryptophan, could break the tolerogenic state that protects the allogeneic conceptus from the maternal immune system³¹. A critical role for IDO1 in immunomodulation has been confirmed in numerous animal models, including models of allograft tolerance, inflammation, and cancer²⁵. While IDO1 inhibition can exacerbate disease in models of autoimmune disorders²⁵, IDO1 null mice show no evidence of susceptibility to developing spontaneous autoimmunity or alterations in immune system development²⁷, suggesting that IDO1 inhibition, in a therapeutic setting, may produce minimal side effects in subjects without pre-existing autoimmune conditions.

Within the context of cancer, there are several lines of evidence to suggest that IDO1 is a key regulator of the immunosuppressive mechanisms responsible for tumor escape from immune surveillance. Several groups have demonstrated that blockade of IDO1 activity can directly influence the ability of tumor-bearing animals to reject tumors^{32,33}. In addition, studies with 1-methyl-tryptophan demonstrate that IDO1 inhibition dramatically increases the efficacy of various chemotherapeutic agents (eg, platinum compounds, taxane derivatives, cyclophosphamide) without increased toxicity³³. Although the specific mechanisms responsible for this potentiation remain to be fully elucidated, the effects were not observed in T-cell–deficient animals, suggesting

that the results may be the consequence of the disablement of immunosuppressive mechanisms that exist within the tumor microenvironment.

Based on studies examining serum levels of tryptophan and kynurenine, IDO1 appears to be chronically activated in patients with cancer, and IDO1 activation correlates with more extensive disease^{34,35}. Indoleamine 2,3-dioxygenase 1 has subsequently been found to be overexpressed by a wide variety of human tumor cell types, as well as by the DCs that localize to the tumor-draining lymph nodes^{25,32}. Increased expression of IDO1 in tumor cells has been shown to be an independent prognostic variable for reduced overall survival (OS) in subjects with melanoma, ovarian, colorectal, and pancreatic cancers³⁶⁻⁴⁰.

Together, these results suggest that the IDO1 pathway is a key regulatory element responsible for the induction and maintenance of tumor immune tolerance. Small molecule inhibitors of IDO1 may provide an innovative and tractable method to treat malignancies either alone or in combination with chemotherapeutics and/or immunotherapy-based strategies.

EPACADOSTAT: BACKGROUND

Mechanism of Action

Epacadostat represents a novel, potent, and selective inhibitor of the enzyme indoleamine 2,3-dioxygenase 1 (IDO1) in both human tumor cells and human dendritic cells (DCs).

Pharmaceutical and Preclinical Background

For a thorough discussion of the pharmacology and preclinical background of epacadostat, refer to the epacadostat Investigator's Brochure, Sections 3.0 and 4.0

Epacadostat: Clinical safety data

Combination Therapy

As of the data cut off (28 MAR 2016), 60 subjects have been enrolled in INCB 24360-202 (epacadostat 25 mg, 50 mg, 100 mg, and 300 mg BID in combination with pembrolizumab). Based on the preliminary unaudited safety data (unaudited), no Grade 4 treatment related AEs were reported. Three subjects (5%) discontinued for a treatment-related AE: Grade 3 arthralgia, Grade 3 AST elevation, and Grade 2 nervous system disorder. No treatment-related deaths occurred. Treatment-emergent AEs were reported in 44 subjects (73.0%). The most frequently reported AEs were rash (27%) followed by fatigue (23%). Rash includes the preferred terms rash, rash generalized, rash maculopapular, rash pruritic, and rash follicular. As of the data cutoff (28 MAR 2016), 18 subjects in the Phase 1 portion of the INCB 24360-202 study and 119 subjects in the Phase 2 portion of the study have received combination treatment with pembrolizumab and the 100 mg BID dose of epacadostat, the recommended dose for the Phase 3 study. The data for Phase 2 presents a subset of 99 subjects who had at least 1 month of safety data. The most frequently reported ($\geq 15\%$) AEs of any grade for the combined Phase 1 and Phase 2 subjects treated with epacadostat 100 mg BID were fatigue (35.0%), constipation (24.8%), diarrhea (20.5%), nausea (20.5%), vomiting (18.8%), pyrexia (16.2%), and dyspnea (15.4%). Fatigue (13.7%) and rash (11.1%; including the preferred terms rash, rash maculopapular, rash generalized, and rash macular) were the only treatment-related AEs reported in $> 10\%$ of subjects. Treatment-related AEs of rash were only reported in Phase 2. Treatment-related AEs \geq Grade 3 occurring in more than 1 subject who received epacadostat 100 mg BID in Phase 1 or Phase 2 included rash (5 subjects, 4.3%) and dehydration, lipase increased, AST increased, and nausea (2 subjects [1.7%] each).

For a thorough discussion of the pharmacology and preclinical background of epacadostat, refer to the epacadostat Investigator's Brochure, Sections 6.0 and 7.0

Clinical efficacy data for epacadostat in combination with pembrolizumab in HNSCC

Efficacy

Epacadostat was tested in combination with the PD-1 antibody pembrolizumab in 38 patients with SCCHN as part of a phase 1 / 2 clinical trial. Objective responses were seen in 11 of 36 evaluable patients (30.5%) and disease stabilization was observed in 10 additional patients for an overall disease control rate of 58.3%¹⁷.

Rationale for the Proposed Study

Anti-PD1 antibodies induce durable remissions in only 12-20% of patients with unresectable SCCHN^{2,3}. HNSCC patients, who lack tumor-infiltrating lymphocytes (TILs) and the associated IFN- γ -gene signature are extremely unlikely to respond to anti-PD-1⁴. Interleukin-12 (IL-12) promotes a pro-inflammatory tumor environment, enhanced antigen presentation, Th1 polarization, an increased frequency of TIL and ultimately productive systemic anti-tumor immune responses. When IL-12 is administered systemically, it can be toxic⁵, but intratumoral electroporation of plasmid IL-12 (tavokinogene telseplasmid or tavo-EP) leads to sustained IL-12 exposure in the tumor microenvironment, priming immune responses and leading to regression of both treated and untreated lesions in the absence of systemic therapy. tavo-EP demonstrates substantial clinical synergy with the PD-1 antibody, pembrolizumab, and even non-responders often demonstrated an increase in TILs both in treated and untreated lesions. However, the balance between effector CD8⁺ T cells is skewed towards suppressive leukocytes (PD-L1⁺CD163⁺ monocytes and FoxP3⁺ Tregs) in non-responders. Epacadostat is an oral IDO1 inhibitor that increases proliferation and activation of effector cells including NK cells, DCs, and T lymphocytes while depleting Tregs. Our data thus far also suggest that effective anticancer immune responses require 3 steps: 1) immune priming and tumor infiltration with T cells; 2) activation of partially exhausted TILs; and 3) selective modulation of T cell populations to maximize the CD8⁺ T_E : Treg ratio. Based on the results of the clinical and translational data in Stage 1, Stage 2 will be developed in consultation with the Principal Investigator and leadership from both OncoSec and Incyte. Which will be submitted to the local and federal regulatory bodies for review and approval prior to being implemented.

2 Objectives of the Study

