Dose Escalation Safety Lead-In and Mid-Study Interim Safety Analysis	
Dose Escalation Safety Lead-In
 
1. If, at any time, 1 or more of the first 3 safety-evaluable patients experience grade 3 or higher treatment-associated adverse events within the first 30 days of initiation of treatment, then no further patients will be enrolled at the current dose level.2. After 6 patients have been enrolled on study, enrollment will be halted for 30 days for completion of the dose escalation lead-in safety analysis. If 0-1 patients experience grade 3 or higher treatment-associated adverse events within the first 30 days of initiation of treatment, then additional patients may be enrolled at the next dose level.3. If enrollment is halted at any time during the lead-in period due to treatment-associated adverse events, the UCSF DSMB will review all available safety data with the Principal Investigator. Based on this review, study discontinuation or reduction of the epacadostat dose may be recommended. No further patients will be enrolled on study without the approval of the DSMB. If the DSMB allows additional patients to enroll, the lead-in period will be repeated at the new dose level with a maximum of 6 additional patients enrolled prior to follow-up safety analysis. At the discretion of the DSMB, patients who are currently on study may continue treatment at the reduced dose level.4. Patients who discontinue treatment on study within 30 days of initiation of therapy for reasons other than treatment-associated toxicity will be deemed inevaluable for safety and replaced for safety analysis. 
Mid-Study Interim Safety Analysis (Stage 1)
 
Enrollment will also be halted for 30 days for interim safety analyses after a total of 30 safety-evaluable patients have initiated treatment on study in both Arms A and B. Patients who discontinue treatment on study within 30 days of initiation of therapy for reasons other than treatment-associated toxicity will be deemed inevaluable for safety and replaced for safety analysis. The study will be discontinued under the following circumstance:
 
1. On-study occurrence of 3 or more Grade 4 (life threatening) serious adverse events (SAEs) or deaths, which are deemed at least possibly related to the study agent.2. Based on the review of data the DSMB has serious concerns about the safety of patients on the study. In addition to stopping the study, the DSMB may recommend that the epacadostat dose for all patients be de-escalated for all current and future patients or cessation of further patient accrual.

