- ⁸ Fresh biopsy collection will be done at screening, Cycle 2 Day 1, and at progression/end of treatment. Additional biopsies may be performed if clinically indicated.
- ⁹ Research blood requirements are described in *Section 10*. Mandatory blood collection will occur on Cycle 2, Day 1; Optional sample collection will occur on Day 22 for Cycles 2 and beyond and then on Day 1 for Cycles 3 and beyond. Additional research blood acquisition, storage, and distribution information is provided in *Section 10*. Every effort shall be made to collect mandatory post-treatment (follow-up) research blood samples, but failure to collect this sample due to patient refusal or logistical constraints shall not constitute a protocol deviation or violation.
- ¹⁰ MRI, contrast-enhanced CT, or PET/CT imaging of the face, neck, chest, abdomen, and pelvis are required at screening and on day 1 of each odd-numbered cycle excluding cycle 1. Both clinical and radiographic measurements may be used. All superficial, clinically apparent lesions that cannot be adequately assessed radiographically (e. g. subcutaneous lesions) must be numbered and photographed with a metric ruler visible in each photograph. For photographed lesions with borders that are not clearly visible, investigators should trace the lesions' outline, making a solid line with a felt-tipped pen. Visible lesions should never be circled with a solid line but dashed or dotted lines may be used to distinguish these markings from the borders of otherwise invisible lesions. Tumor assessments will be made using RECIST version 1.1. IL-12 plasmid dosing may be based on the most recent tumor measurements and measurements need not be repeated immediately prior to each tavo-EP treatment.
- ¹¹ Epacadostat dose may be changed if indicated based on dose escalation safety run-in described below in Table 4-1.

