7.1 Sample Size Justification

Dose Expansion Phase, Stage 1: We expect to enroll 30 patients in both arms (15 patients in Arm A and 15 patients in Arm B). We will allow patients who were enrolled in the dose escalation safety lead-in to enroll in Arm A of Stage 1, depending on the final dose.

Dose Expansion Phase, Stage 2: Depending on the results of the clinical data in Stage 1, Stage 2 will enroll up to an additional 26 patients accordingly:

If there are at least ≥ 3 responses in 15 patients, in either Arms A or B, up to an additional 26 patients (13 patients in Arm A and 13 patients in Arm B) will be enrolled in the respective treatment arms.

The above Simon 2-stage sample sizes were based on the following assumptions: the objective response rate for pembrolizumab is approximately 15%³ and we suggest that a 20% absolute improvement in this response rate would be clinically meaningful. We propose to test the hypothesis that the objective response rate for the combination of tavo-EP with pembrolizumab and epacadostat is 35% versus the null hypothesis that it is similar to the response rate for pembrolizumab monotherapy, 15%. The statistical power calculations are based on the Simon Two-Stage Optimal Design¹¹ with a Type I error rate of 0.05 and power of 80%.

Efficacy Assessment:

The objective response rate for pembrolizumab is approximately 15%³ and we suggest that a 20% absolute improvement in this response rate would be clinically meaningful. We propose to test the hypothesis that the objective response rate for the combination of tavo-EP with pembrolizumab and epacadostat is 35% versus the null hypothesis that it is similar

to the response rate for pembrolizumab monotherapy, 15%. The following statistical power calculations are based on the Simon Two-Stage Optimal Design¹¹ with a Type I error rate of 0.05 and power of 80%.

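### Stage 2 is both fixed in advance and still to be developed, its gate does not clearly judge each arm on its own results, and the time at which the gate is read is undefined

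*Combined protocol and SAP*

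**What the plan says.** Four places set Stage 2 in advance: the synopsis rows on study design, duration of therapy and sample size, and Section 7.1. Section 7.1 reads: "If there are at least ≥ 3 responses in 15 patients, in either Arms A or B, up to an additional 26 patients". It then splits the 26 into 13 for Arm A and 13 for Arm B, to be enrolled in the respective arms. The study design row applies this rule at the conclusion of Stage 1. The sizes are presented as a Simon two-stage design testing 35% against 15%, "with a Type I error rate of 0.05 and power of 80" percent. Section 7.3 uses BORR to run that design. The synopsis and Section 2.4 define BORR by confirmed CR or PR.

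The Rationale for the Proposed Study describes something else: "Based on the results of the clinical and translational data in Stage 1, Stage 2 will be developed in consultation with the Principal Investigator" and the leadership of the two companies. The outcome is then to go to local and federal regulatory bodies before use. Section 3.1 says only that Stage 2 depends on Stage 1 clinical data.

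On timing, cycles last 42 days (Table 3-1) and scans "are required at screening and on day 1 of each odd-numbered cycle excluding cycle 1" (footnote 10). Section 6.1.1 requires confirmation at least 4 weeks after a response is first seen and allows it to wait for the next scheduled scan, 12 weeks later. Separately, the synopsis and Section 5.2 state: "Enrollment will also be halted for 30 days for interim safety analyses after a total of 30 safety-evaluable patients have initiated treatment".

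**The concern.** Three things are unsettled about one decision, which is whether up to 26 more patients are enrolled.

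- **Whether Stage 2 is fixed.** A numerical gate with fixed sizes cannot coexist with a Stage 2 written after the clinical and translational data have been seen. Type I error and power computed for a fixed rule do not describe a design chosen from the data.
- **Which arm the gate governs.** The word *either*, followed by patients listed for both arms, can be read as one arm's success opening both. Up to 13 patients could then enter a regimen that its own gate would have stopped.
- **When the gate is read.** A confirmed response takes months to establish, and no assessment marks the end of Stage 1. If the gate is read before all 15 patients in an arm can be judged, those not yet assessed cannot contribute a response.

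**Working it through.** **Inputs.** Null rate 15%, alternative 35%, type I error 0.05, power 80%, 15 patients per arm in Stage 1, gate at 3 or more responses, 13 more per arm (all Section 7.1). Cycle length, scan days and confirmation interval are as cited above. The hypothesis is written for the triplet only. I apply the same rates to Arm B because it has the same sizes and gate. I treat the arms as independent.

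**1. The plan's own figures.** Exact enumeration of two-stage designs gives 15 then 13 patients, stopping at 2 or fewer of 15 and rejecting the null at 8 or more of 28, with type I error 0.0461 and power 0.8027. So the sizes reproduce 0.05 and 80% for one arm with its own gate. The cut-off of 8 of 28 is derived here and is not in the documents. As an aside, this is the minimax design. The optimal one, which the plan names, has 9 patients in Stage 1 and 34 in total.

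**2. Own-arm gate.** P(stop) = P(X ≤ 2) with X ~ Bin(15, p).

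- p = 0.15: 0.85^15 + 15(0.15)(0.85^14) + 105(0.15²)(0.85^13) = 0.604
- p = 0.35: 0.65^15 + 15(0.35)(0.65^14) + 105(0.35²)(0.65^13) = 0.062

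**3. Both-arms gate.** An arm stops only if both arms fail. Expected size is 15 + 13 × (1 − P(stop)). The last column uses the derived cut-off of 8 of 28.

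| Gate, for an arm at 15% | P(stop after Stage 1) | Expected size | Type I error |
|---|---|---|---|
| Own arm only | 0.604 | 20.1 | 0.0461 |
| Either opens both, other arm at 15% | 0.604 × 0.604 = 0.365 | 23.3 | 0.0471 |
| Either opens both, other arm at 35% | 0.604 × 0.062 = 0.037 | 27.5 | 0.0484 |

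With no futility stop at all, P(X ≥ 8) for Bin(28, 0.15) is 0.0486. Relaxing the gate therefore cannot push type I error above 0.05 with this cut-off. Power does not fall either: for an arm at 35% it rises from 0.803 to 0.809 (other arm at 15%) or 0.817 (other arm at 35%).

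**4. Timing on the scheduled scans.**

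- First scan, Cycle 3 Day 1: 1 + 2 × 42 = Day 85.
- Earliest confirmation: 85 + 28 = Day 113 (about Day 110 using the ±3-day window in Section 3.4).
- Next scheduled scan, Cycle 5 Day 1: 1 + 4 × 42 = Day 169.
- The safety halt ends on Day 31 of the 30th patient. For that patient the gap to confirmation is 113 − 31 = 82 days (about 12 weeks), or 169 − 31 = 138 days (about 20 weeks) if confirmation waits for the next scheduled scan.

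**5. Fixed against redesigned Stage 2.** No calculation applies. The Rationale gives no rule for the redesign, so its error rates cannot be computed.

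**The case against.** The arm-by-arm reading of the gate has good support. All four places say *up to* 26 and refer to the *respective* arms, and Section 7.3 analyses by treatment arm. This stands: the text is ambiguous, and a reader who infers that one success plainly opens both arms goes too far. The figures of 0.37 and 0.04 apply only under that reading.

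A reader might also infer that the 30-day halt ends before any confirmed response is possible and so contradicts the gate. The documents do not support this. The halt is a safety analysis, and nothing ties the response gate to its end. It starts only after the 30th patient has begun treatment, so earlier patients, and lead-in patients carried into Arm A, may be well past Day 113. The documents give no accrual rate. If, as an assumption, 68 patients accrue evenly over 12 to 24 months, 14 to 22 of the 30 would have reached Day 113 when the halt ends. What remains is a missing definition.

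Section 11.1.1.1 counts a patient as evaluable for response only after re-evaluation or early progression, which suggests that the gate should use assessed patients. The gate does not cite that definition, however, and Sections 7.2 and 7.3 compute BORR on all treated subjects.

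**Conclusion.** The concern holds in three parts. The conflict between a fixed Stage 2 and one still to be developed is direct, and both statements are current text. The gate is ambiguous. Under the both-arms reading, an inactive arm's chance of stopping falls from 0.60 to 0.37 or 0.04, and its expected size rises by about 3 or 7 patients (23.3 − 20.1 = 3.2; 27.5 − 20.1 = 7.4). The end of Stage 1 has no link to a response assessment.

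A reader might infer that the both-arms reading breaks the type I error claim. It does not: with 8 of 28 as the final cut-off, the error stays at 0.047 to 0.048. What is lost is futility stopping. The claimed error rates are undermined only if Stage 2 is really redesigned on Stage 1 data.

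The figures assume independent arms, rates of 15% and 35% in either arm, and a final cut-off that the plan does not state. The effect of reading the gate early cannot be sized without an accrual rate.

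**What to change.** 1. In the four places that state the gate, say that each arm is judged separately and enrols 13 more patients only if that arm itself has at least 3 confirmed responses in its first 15.
2. Reconcile the Rationale for the Proposed Study with this rule, keeping its commitment to regulatory review before Stage 2. If Stage 2 really is to be redesigned on Stage 1 data, withdraw the two-stage type I error and power claim instead.
3. Define the conclusion of Stage 1 for each arm as the point when all 15 patients are evaluable for confirmed response over a stated window. The window must agree with the BORR definition, which is itself given two ways: over the trial (synopsis, Section 2.4) and over 24 weeks (footnote to Table 6-1).
4. Allow an arm that already has 3 confirmed responses to proceed earlier, but not before the safety halt is complete.

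The cost is wording, plus a possible wait after the safety halt in an arm still below 3 responses. That wait is about 12 weeks, or about 20 if confirmation falls at the next scheduled scan. It is longer if the chosen window also admits responses first seen at the Day 169 scan: 169 + 28 − 31 = 166 days, about 24 weeks.
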